4.3. Additional Information

4.3.1. Site Personnel

A minimum of 3 separate health care professionals (HCPs) are required:

1. A treating HCP (the Principal Investigator [PI] or Sub-investigator) may serve as a treating HCP who is responsible for the following:
 - Administration of Montreal Cognitive Assessment (MOCA) at Day 1 and during management of amyloid-related imaging abnormalities (ARIA) cases.
 - Management of the routine neurological care of the subject.
 - Assessment (including assignment of causality) and treatment of adverse events (AEs).
 - Review of selected hematology and blood chemistry results from the central laboratory to assess if the subject's study treatment should be temporarily withheld or permanently discontinued according to the criteria detailed in Section 10.1.
2. An independent rating HCP (designated by the PI of the site) who is responsible for administering the Clinical Dementia Rating (CDR)
3. A second independent rating HCP (designated by the PI of the site) who will administer the Alzheimer's Disease Assessment Scale-Cognitive Subscale (13 items) [ADAS-Cog 13], Alzheimer's Disease Cooperative Study-Activities of Daily Living Inventory (Mild Cognitive Impairment version) [ADCS-ADL-MCI], and the Mini-Mental State Examination (MMSE)

The 2 independent rating HCPs must not be involved with any other aspect of subject care and management and must remain blinded to AEs, concomitant therapy, laboratory data, imaging data, or any other data that have the potential of revealing the treatment assignment. PIs cannot serve as rating HCPs. The treating HCPs must not discuss AEs (e.g., ARIA) with the independent rating HCPs.

To ensure consistency across sites, rating HCPs must complete the standardized study-specific qualification process on clinical efficacy assessment scoring prior to administration of the specific assessment at their site. All sites should attempt to maintain the same rating HCP throughout the study for specific assessments. Each subject should have the same rating HCP perform the subject's specific rating assessment throughout the study. If a rating HCP has to be replaced, the new rating HCP must undergo the study-specific qualification process prior to administration of the assessment.

Hematology and blood chemistry data will be sent to the investigational sites to aid in management of the subject. As with other laboratory and clinical information, these data should NOT be reviewed by the rating HCPs.

CONFIDENTIAL

The information contained herein may not be used, disclosed, or published without the written consent of Biogen MA Inc.

The roles of independent raters and treating HCP are NOT interchangeable at the subject level. In addition, the 2 independent raters are not interchangeable at the subject level. If a rater has administered the CDR to a subject they may not administer the other neurocognitive assessments to that subject at any point during the study.

An unblinded pharmacist (or authorized designee) will be responsible for the storage, distribution, preparation and accountability of study treatment. The unblinded pharmacist will also be responsible for maintaining the unblinded pharmacy record separate from the main study file in order to support the study blind.

CONFIDENTIAL

The information contained herein may not be used, disclosed, or published without the written consent of Biogen MA Inc.

5. INTRODUCTION

Alzheimer's disease (AD) is the most common cause of dementia, accounting for 50% to 75% of all cases. Alzheimer's Disease International estimates that as of 2013, there were 44.4 million people living with dementia worldwide and that this figure will increase to 135.5 million by 2050 [Alzheimer's Disease International 2014].

Clinically, AD is a progressive neurodegenerative disorder characterized by an insidious and unrelenting decline in cognition and behavioral disturbances that result in the person's inability to perform usual activities of daily living [Jack 2013].

Pathologically, AD is defined by the presence in the brain of extracellular neuritic plaques containing β -amyloid ($A\beta$) peptide and intraneuronal neurofibrillary tangles composed of hyperphosphorylated tau proteins. The pathogenesis of these plaques and tangles and how they contribute to the clinical syndrome remain to be fully elucidated, but the leading hypothesis — the "amyloid cascade" — proposes that the driving force behind the disease process is the accumulation of $A\beta$ resulting from an imbalance between $A\beta$ production and $A\beta$ clearance in the brain [Hardy and Selkoe 2002].

The current view of AD, the disease process and its clinical manifestations, is that it manifests along a continuum rather than having categorical stages. Evidence suggests the pathophysiological changes begin years before clinical onset and as the disease progresses cognitive impairments, behavioral changes, and functional disability manifest [Jack 2013]. Revised criteria for the clinical diagnosis of AD were published by the National Institute on Aging (NIA) and the Alzheimer's Association (AA) [Albert 2011; McKhann 2011; Sperling 2011] and the International Working Group (IWG) [Dubois 2010; Dubois 2014], and a group that included members from both NIA-AA and IWG published recommendations to harmonize the criteria [Morris 2014]. These criteria base the diagnosis of AD on both clinical and biological elements, recognizing the existence of a nonclinical stage of the disease by accepting AD diagnoses prior to signs of dementia using AD biomarkers.

The scientific community has shifted its focus to target patients in the earlier course of the disease continuum with the belief that those patients are more likely to benefit from anti-amyloid therapy. Supporting this hypothesis are results from solanezumab and crenezumab studies that have shown a trend in slowing cognitive decline in mild but not moderate AD [Doody 2014; Fagan 2014].

There are currently no therapies that modify the course of AD, but several potential disease-modifying drug candidates are under investigation. These candidates include small molecules and immunotherapy (active and passive) that target the $A\beta$ pathway and aim to provide therapeutic benefit by reducing either soluble or insoluble forms of $A\beta$ in the brain and cerebrospinal fluid (CSF). Aducanumab is a human monoclonal antibody that recognizes aggregated forms of $A\beta$, including soluble $A\beta$ oligomers and deposited fibrillar $A\beta$. Earlier publications have reported on results that demonstrated in the brain of an animal model of AD that both soluble oligomers and amyloid plaques are neurotoxic [Koffie 2009; Kuchibhotla 2008; Meyer-Luehmann 2008] and clearance of amyloid plaques could lead to normalization of

CONFIDENTIAL

The information contained herein may not be used, disclosed, or published without the written consent of Biogen MA Inc.

calcium homeostasis and neuronal activity, as well as reduction of oxidative stress [Rozkalne 2009; Spires-Jones 2009]. Similarly, patients with AD who generated anti-A β antibodies after active immunization with aggregated A β (42) showed slower rates of decline of cognitive function and activities of daily living [Hock 2003].

5.1. Profile of Previous Experience With Aducanumab

5.1.1. Nonclinical Experience

Aducanumab is a unique human, anti-A β monoclonal antibody identified and derived from B lymphocytes using the reverse translational medicine approach. Using this technique, immune repertoires obtained from cohorts of healthy elderly human donors with excellent cognitive performance or with impaired but stable courses were screened for memory B cells against aggregated A β .

In vitro studies have demonstrated that aducanumab and its analogs are highly selective for soluble oligomeric and insoluble fibrillar forms of A β relative to soluble low-molecular-weight forms of A β . In vivo pharmacology studies indicated that a murine immunoglobulin (Ig) G2a chimeric version of the antibody (ch12F6A) with similar properties significantly reduced amyloid plaque burden in the brains of aged Tg2576 mice, a mouse model of AD, through a microglia-mediated phagocytic mechanism. These data suggest aducanumab could provide benefit by reducing plaque burden.

The toxicokinetic profile of aducanumab was evaluated in Tg2576 mice in 13-week and 6-month studies and in cynomolgus monkeys in a 4-week study. Of the 2 species, the Tg2576 mouse is considered the primary pharmacologically relevant species given that these mice accumulate amyloid plaques in the cerebral parenchyma and vasculature. In addition to the standard histopathological evaluation in mice, Perls' staining of hemosiderin (a breakdown product of hemoglobin) was performed to quantify microhemorrhage. Microhemorrhage has been observed both as a background finding in transgenic mouse models of AD [Winkler 2001], including Tg2576 mice [Kumar-Singh 2005], and as a drug-related finding in transgenic mice treated with some anti-A β antibodies [Pfeifer 2002; Racke 2005; Wilcock and Colton 2009].

Findings consistent with amyloid plaques and vascular amyloid were identified in the brain sections of animals in all groups, including the control group, as expected with this model. In both studies, repeated administration of ch12F6A or aducanumab was well tolerated with no treatment-related deaths observed during the dosing period. In the 13-week toxicology study, meningeal/cerebral vascular inflammation and/or vascular thickening were observed in mice dosed with ch12F6A ≥ 70 mg/kg compared with the control group. In the 6-month study, although slight differences were observed between ch12F6A-treated groups and the control group, animals treated with aducanumab were comparable to the control animals. The evaluation of microhemorrhage, characterized by quantification of hemosiderin in Perls stained brain sections of each main study and recovery animal, demonstrated no significant increase in scores with ch12F6A or aducanumab treatment in either study. The incidence and severity of hemorrhage or cerebral vascular inflammation were comparable in the 13-week and 6-month mouse studies.

CONFIDENTIAL

The information contained herein may not be used, disclosed, or published without the written consent of Biogen MA Inc.

See the Investigator's Brochure (IB) for detailed information on nonclinical studies.

5.1.2. Clinical Experience

Aducanumab has been evaluated in one completed single ascending dose study (221AD101) and one ongoing multiple ascending dose study (221AD103):

- Study 221AD101 was a Phase 1, randomized, double-blind, placebo-controlled, study of aducanumab in subjects with mild or moderate AD.

The primary objective was to evaluate the safety and tolerability of a range of aducanumab doses (0.3 to 60 mg/kg) when administered as single intravenous (IV) infusions. The secondary objectives were to assess the pharmacokinetic (PK) and immunogenicity of aducanumab after single-dose administration.

A single dose of aducanumab up to 30 mg/kg was demonstrated to be well tolerated. Dose-limiting ARIA (2 subjects with ARIA-E [edema] and 1 subject with ARIA-E and ARIA-H [microhemorrhage]) was observed in the 60 mg/kg dose group resulting in termination of further dosing in that cohort; no cases of ARIA were observed at single doses below 60 mg/kg. The PK profile was dose linear.

- Study 221AD103 is an ongoing randomized, double-blind, placebo-controlled multiple dose study of aducanumab in subjects with prodromal or mild AD who are amyloid positive. The study comprises a placebo-controlled period with subjects receiving monthly doses of aducanumab (fixed doses of 1, 3, 6, or 10 mg/kg, or titration up to 6 mg/kg) or placebo for a year followed by a dose-blind long-term extension (LTE) period with subjects receiving monthly doses of aducanumab.

The primary objective of Study 221AD103 is to evaluate the safety and tolerability of multiple doses of aducanumab administered monthly as single IV infusions. The secondary objectives are to assess the effect of aducanumab on cerebral amyloid plaque content as measured by ¹⁸F-florbetapir positron emission tomography (PET), and to evaluate the PK and immunogenicity of aducanumab after multiple-dose administration. Exploratory objectives include assessment of the effect of aducanumab on the clinical progression of AD as measured by CDR-sum of boxes (SB) and MMSE.

To date, ARIA has been the most frequent AE reported in the study. ARIA-E was radiographically monitored by magnetic resonance imaging (MRI) and typically observed early in treatment (between 2 to 5 doses). In most cases, ARIA-E resolved 4 to 12 weeks after onset and ARIA-H was typically stable 2 to 4 weeks after onset. Incidence of ARIA has been observed to be both dose and Apolipoprotein E4 (ApoE ε4) carriage-dependent, especially at the highest doses (refer to the IB for details on events of ARIA).

Protocol-defined interim analyses have demonstrated a dose- and time-dependent reduction of brain amyloid burden after 6 months of dosing (Week 26), with statistical significance achieved in the 3, 6, and 10 mg/kg groups compared with placebo, and after 1 year of dosing (Week 54), with statistical significance achieved

CONFIDENTIAL

The information contained herein may not be used, disclosed, or published without the written consent of Biogen MA Inc.

in the 3 and 10 mg/kg groups compared with placebo (see current IB for results of the most recent interim analysis). The results demonstrate target engagement (amyloid plaques) and a pharmacodynamic effect (dose-dependent amyloid reduction). In addition results from the interim analyses showed an effect at 1 year on the exploratory endpoints CDR-SB and MMSE, suggesting a reduction in the progression of clinical impairment for aducanumab-treated versus placebo-treated subjects. At Week 54, adjusted mean change (increase) from baseline in CDR-SB score was smaller for both the 3 and 10 mg/kg groups compared with placebo, with statistical significance achieved in the 10 mg/kg group (see current IB for results of the most recent interim analysis). At Week 52, adjusted mean changes (decreases) in MMSE score from baseline were statistically significant in the 3 and 10 mg/kg groups (see current IB for results of the most recent interim analysis). Refer to the IB for details on interim analyses results.

5.2. Study Rationale

The purpose of this study is to assess the efficacy and safety of aducanumab compared with placebo in subjects with early AD including subjects with mild cognitive impairment (MCI) due to AD and a subset of mild AD. Aducanumab is a human monoclonal antibody that recognizes aggregated forms of A β , including soluble A β oligomers and deposited fibrillar A β . Earlier publications have demonstrated that both soluble oligomers and amyloid plaques are neurotoxic [Koffie 2009; Kuchibhotla 2008; Meyer-Luehmann 2008] and clearance of amyloid plaques could lead to normalization of calcium homeostasis and neuronal activity, as well as reduction of oxidative stress in the brain of an animal model of AD [Rozkalne 2009; Spires-Jones 2009]. For this reason, treatment with aducanumab is expected to slow progression of AD, while preserving global function longer, when compared with untreated subjects.

Interim analyses of the ongoing multiple dose study (Study 221AD103) have demonstrated target engagement, a PD effect on amyloid reduction, and an effect on CDR-SB and MMSE suggestive of a reduction in the progression of clinical impairment for aducanumab-treated subjects. These results along with the observed safety and tolerability profile warrant the further Phase 3 investigation of aducanumab in a patient population spanning the early stages of the AD continuum.

5.3. Rationale for Dose and Schedule Selection

The dosing regimen selected for this study was based on the PK and PD relationship for removal of brain amyloid and effect on CDR-SB and MMSE observed in Study 221AD103 interim analyses and on safety, tolerability, and PK data from studies 221AD101 (complete) and 221AD103 (ongoing).

The dose- and time-dependent reduction of brain amyloid burden observed with aducanumab treatment was statistically significant at doses of 3, 6 and 10 mg/kg after 6 months of dosing and at 3 and 10 mg/kg after 12 months of dosing (see current IB for results of the most recent interim analysis). The effect on mean decrease from baseline in CDR-SB after 12 months of dosing was observed at both 3 and 10 mg/kg (see current IB for results of the most recent interim analysis).

CONFIDENTIAL

The information contained herein may not be used, disclosed, or published without the written consent of Biogen MA Inc.

with statistical significance achieved at 10 mg/kg. The effect on mean decrease from baseline in MMSE score was statistically significant at 3 and 10 mg/kg. These data indicate that 3 mg/kg could be considered an acceptable dose for Phase 3 studies; however, given the dose-dependent nature of these observations, the use of higher doses (6 and 10 mg/kg) could offer greater benefit at acceptable risk.

ARIA has been identified as an event that may occur with anti-amyloid targeting drug candidates and is considered an event of special interest in the aducanumab program. To date, the incidence of ARIA has been observed to be both dose and ApoE ϵ 4 carriage dependent, especially at the highest doses. In an effort to maximize the dose-dependent amyloid reduction and effect on CDR-SB and MMSE that have been observed with doses of 3 mg/kg and higher while maintaining ARIA incidence, severity, and related discontinuation rate within acceptable levels, a titration regimen will be explored. It has been suggested that the ARIA observed following treatment with amyloid targeting agents may be due, in part, to the initial large removal of amyloid and subsequent saturation of perivascular brain amyloid clearance mechanisms [Weller 2008]. Slow titration to the target dose is expected to result in slower initial amyloid removal, yet trigger alternative mechanisms of amyloid clearance including monoclonal antibody-dependent Fc-mediated microglial clearance [Ostrowitzki 2012] which would prevent saturation of amyloid clearance and subsequent ARIA during titration and once the target dose is reached. Since aducanumab-induced ARIA has been demonstrated to occur early during treatment, with most cases occurring within the first 5 doses, titration of aducanumab for up to 6 doses prior to reaching the target dose may result in reduction of ARIA incidence and severity.

Given the tolerability and apparent efficacy of aducanumab shown to date, the doses to be tested using a titration regimen are 3 and 6 mg/kg for ApoE ϵ 4 carriers, and 6 and 10 mg/kg for ApoE ϵ 4 non-carriers. Titration will start at 1 mg/kg and will escalate to 3, 6 and 10 mg/kg as detailed below.

5.3.1. Dosing Scheme

5.3.1.1. Placebo-Controlled Period

Doses will be administered approximately 4 weeks apart, over approximately 76 weeks (a total of 20 doses). Based upon their ApoE ϵ 4 carrier status, subjects will be assigned to 1 of 3 treatment groups (450 subjects each) in a 1:1:1 ratio (aducanumab low dose: aducanumab high dose: placebo) as follows (Table 7 and Figure 1):

ApoE ϵ 4 Carrier

- Low dose (3 mg/kg)
1 mg/kg for the first 2 doses, 3 mg/kg thereafter
- High dose (6 mg/kg)
1 mg/kg for the first 2 doses, 3 mg/kg for the next 4 doses, and 6 mg/kg thereafter
- Placebo
Saline infusion

CONFIDENTIAL

The information contained herein may not be used, disclosed, or published without the written consent of Biogen MA Inc.

ApoE ε4 Non-Carrier

- Low dose (6 mg/kg)
1 mg/kg for the first 2 doses, 3 mg/kg for the next 4 doses, and 6 mg/kg thereafter
- High dose (10 mg/kg)
1 mg/kg for the first 2 doses, 3 mg/kg for the next 2 doses, 6 mg/kg for the next 2 doses, and 10 mg/kg thereafter
- Placebo
Saline infusion

Table 7: Dosing Scheme for Aducanumab by Regimen

Dose (Month)		1	2	3	4	5	6	7 to 20
Regimen		Dose (mg/kg)						
ApoE ε4 (+)	Low Dose	1	1	3	3	3	3	3
	High Dose	1	1	3	3	3	3	6
	Placebo	saline						
ApoE ε4 (-)	Low Dose	1	1	3	3	3	3	6
	High Dose	1	1	3	3	6	6	10
	Placebo	saline						

5.3.2. Dosing Scheme Modification

An independent data monitoring committee (IDMC) will review unblinded safety data, including serious AEs (SAEs) and incident cases of ARIA, from all ongoing aducanumab studies (e.g., Studies 221AD103, 221AD104, 221AD301, and 221AD302) as described in the IDMC charter.

The dosing scheme can be modified in the following circumstances:

- Safety and tolerability of the high dose
If any of the high doses proposed (10 mg/kg in ApoE ε4 non-carriers and 6 mg/kg in ApoE ε4 carriers) is deemed not acceptable, enrollment for the high dose group(s) will be terminated and subjects will not be replaced. Subjects who have already been randomized to the discontinued dose will be down-dosed to the next available dose according to their ApoE ε4 carrier status. Definition of low and high dose regimens will be revised as described in Section 16.

CONFIDENTIAL

The information contained herein may not be used, disclosed, or published without the written consent of Biogen MA Inc.

- **Benefit of titration**

A titration schedule has been implemented in this Phase 3 study and in the ongoing multiple-dose Study 221AD103. If, based upon review of the data from Study 221AD103, titration is not deemed beneficial, it will be eliminated, and subsequently enrolled subjects who are ApoE ϵ 4 carriers will receive a fixed dose of 3 or 6 mg/kg and non-carriers will receive 6 or 10 mg/kg.

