16.2.2.2. Dose Regimens to be Evaluated

The following dose regimens of aducanumab as compared with placebo will be evaluated:

- Aducanumab high-dose regimen (10 mg/kg in ApoE ϵ 4 [including 6 mg/kg for subjects enrolled under protocol version 1-3 who do not have the opportunity to up-titrate to 10 mg/kg prior to completing Week 78 of the study] and 10 mg/kg in ApoE ϵ 4 non carriers).
- Aducanumab low-dose regimen (3 mg/kg in ApoE ϵ 4 carriers and 6 mg/kg in ApoE ϵ 4 non-carriers).

In the event that the maximum dose (10mg/kg) is terminated after the start of the study (Section 5.3.2) the definition of aducanumab high dose regimen and aducanumab low dose regimen will be modified as shown in Table 12. The dosing modification will be entirely based on interim analysis of outcomes that are independent of, and uninformative about, the treatment-related efficacy effect. Control of Type I error rate is thus maintained without a statistical adjustment for such adaptations[Chow and Chang 2011].

CONFIDENTIAL

The information contained herein may not be used, disclosed, or published without the written consent of Biogen MA Inc.

Table 12: Dose Group Pooling Strategy in the Event of Treatment Group Termination

Treatment Group(s) Terminated	Definitions of Revised Pooled Treatment Groups for Comparison
ApoE ε4 carrier high-dose group (10 mg/kg) [including 6 mg/kg for subjects enrolled under protocol version 1-3 who do not have the opportunity to up-titrate to 10 mg/kg prior to completing Week 78 of the study]	Low: ApoE ε4 carrier 3 mg/kg and non-carrier 6 mg/kg High: ApoE ε4 carrier 3 mg/kg and non-carrier 10 mg/kg
ApoE ε4 non-carrier high-dose group (10 mg/kg)	Low: ApoE ε4 carrier 3 mg/kg and non-carrier 6 mg/kg High: ApoE ε4 carrier 10 mg/kg and non-carrier 6 mg/kg
ApoE ε4 carrier high-dose group (10 mg/kg) AND ApoE ε4 non-carrier high-dose group (10 mg/kg)	ApoE ε4 carrier 3 mg/kg and non-carrier 6 mg/kg

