16.2.2.4. Analysis of the Primary Endpoint

The population for the primary endpoint analysis will be subjects in the ITT population with a baseline and at least one post-baseline CDR-SB score. A mixed model repeated measures (MMRM) model will be used as the primary analysis to analyze change from baseline CDR-SB using fixed effects of treatment, time, treatment-by-time interaction, baseline CDR-SB, baseline CDR-SB by time, baseline MMSE, and baseline ApoE ε4 status.

CONFIDENTIAL

The information contained herein may not be used, disclosed, or published without the written consent of Biogen MA Inc.

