9.2. Randomization and Registration of Subjects

Subjects will be registered at the Screening Visit and randomized only after all baseline assessments have been completed and the Investigator has verified that the subjects are eligible per criteria in Sections 8.1 and 8.2. No subject may begin treatment prior to assignment of a unique identification number (registration) and randomization. Any subject identification numbers or randomization schedule assignments that are assigned will not be reused even if the subject does not receive treatment. Rescreened subjects will be assigned a new number.

Subjects will be randomized to receive aducanumab low dose; aducanumab high dose; placebo in a 1:1:1 ratio. The randomization will be stratified by site and ApoE ϵ 4 status (carrier or non-carrier), so that approximately 60% to 70% ApoE ϵ 4 carriers are enrolled. Enrollment will also be monitored, via the IRT, such that the population of subjects with mild AD represents a small percentage of the total enrolled in the trial. Subjects who withdraw from the study may not be replaced.

Refer to the Study Reference Guide for details on registration and randomization.

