16.7. Sample Size Considerations

The study's sample size is based, in part, on results from a protocol-specified interim analysis from Study 221AD103 which included 1 year data from 1, 3 and 10 mg/kg treatment groups.

A sample size of 450 subjects per treatment group will have approximately 90% power to detect a true mean difference of 0.5 in change from baseline CDR-SB at Week 78 between the 2 treatment groups. This power calculation is based on a 2-sided t-test assuming equal variance with a final significance level of 0.05, a SD of 1.92 and a drop-out rate of 30%. The SD estimate of 1.92 for Week 78 reflects a 39% increase over the SD from the protocol-specified interim analysis of 1-year data.

The assumed true mean difference of 0.5 between the 2 treatment groups represents an approximately 25% reduction in the placebo mean change from baseline at Week 78 if the placebo mean change is estimated to be 2.

The sample size may be reassessed in a blinded manner approximately 3 months before enrollment is complete if at least 15% of the data are available on the primary endpoint. At this interim time-point, the SD for the primary endpoint will be estimated based on the blinded data. The sample size may be increased if the SD is estimated to be more than approximately 2.07. In addition, the sample size could be increased using external clinical trial results that become available after the start of the study.

CONFIDENTIAL

The information contained herein may not be used, disclosed, or published without the written consent of Biogen MA Inc.

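### If a high-dose group is closed, the protocol's no-adjustment claim for Type I error does not cover comparison with placebo subjects randomised after closure

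*Protocol*

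**What the plan says.** - Allocation (Section 9.2): "Subjects will be randomized to receive aducanumab low dose; aducanumab high dose; placebo in a 1:1:1 ratio". On strata: "The randomization will be stratified by site and ApoE" ε4 status. Enrolment period is not a stratum.
- Closure (Section 5.3.2, shown for versions 1.0 to 3.0): "enrollment for the high dose group(s) will be terminated and subjects will not be replaced". Subjects already randomised to the closed dose move to a lower one. No allocation ratio after closure is given.
- Regrouping (Section 16.2.2.2, Table 12): the active regimens are redefined and placebo is not. If the carrier high-dose group closes, revised High is carriers at 3 mg/kg with non-carriers at 10 mg/kg. If both close, a single regimen remains.
- Type I error (Section 16.2.2.2): the stated ground is that the decision to modify dosing uses no information on efficacy. The conclusion drawn is: "Control of Type I error rate is thus maintained without a statistical adjustment for such adaptations". This stands in the latest Section 16 shown, the one that sets 10 mg/kg as the carrier high dose.
- Analysis (Sections 16.2.1 and 16.2.2.4): everyone randomised and dosed, in the randomised group, with a baseline and a post-baseline CDR-SB score. The MMRM terms are treatment, time and their interaction, baseline CDR-SB, "baseline CDR-SB by time, baseline MMSE, and baseline ApoE" ε4 status. Time here is study visit, so no term marks when a subject was enrolled.

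**The concern.** The Type I statement has a sound premise and a conclusion that goes further than the premise. Closing a group on safety data alone does prevent selection on efficacy. It does not make subjects randomised to high dose, all enrolled before closure, comparable with placebo subjects enrolled after it. Those later placebo subjects had no chance of high dose, so they are not randomised controls for it.

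If both groups close and active subjects are pooled, active to placebo is 2:1 before closure and 1:1 after (taking equal low-dose and placebo allocation to continue), so treatment is partly confounded with enrolment period.

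Any difference in progression between early and late enrolees that baseline CDR-SB, MMSE and ApoE status do not absorb enters the contrast. Faster decline in later enrolees makes placebo look worse and favours the drug. Slower decline works against it. Closure was foreseen and given its own table, so the protocol's statement is the rule that would be followed.

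**Working it through.** **The plan's own figure.** Section 16.7: "A sample size of 450 subjects per treatment group will have approximately 90% power to detect a true mean difference of 0.5". The inputs given there are a two-sided test at 0.05, SD 1.92 and 30% drop-out. Evaluable per group: 450 × 0.70 = 315. SE = 1.92 × √(2/315) = 0.153. Power = Φ(0.5/0.153 − 1.96) = 0.905. The stated 90% is reproduced.

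**Assumptions the documents do not supply.** Closure when half of each group has been randomised; equal low-dose and placebo allocation in the closed stratum afterwards, up to 450 each; 65% carriers (the plan gives 60% to 70%); a shift d in mean Week 78 change between early and late enrolees that remains after baseline adjustment. Type I error = P(|Z + bias/SE| > 1.96).

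**Case 1. Carrier group closes; revised High carriers are only those randomised to high dose.** Carriers: 146 high and 292 placebo randomised (102.4 and 204.75 evaluable). Non-carriers: 158 per arm (110.25 evaluable).
- Variance in carriers: 1.92² × (1/102.4 + 1/204.75) = 0.0540. In non-carriers: 1.92² × 2/110.25 = 0.0669.
- Carrier weight: (1/0.0540)/(1/0.0540 + 1/0.0669) = 0.55. SE = 0.173.
- Late share among carriers: placebo 1/2, high 0. Bias = 0.55 × 0.5 × d = 0.28d.

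**Case 2. The same closure; all carriers on 3 mg/kg count as High.** Carriers: 438 active against 292 placebo. Late share 1/3 against 1/2, a difference of 1/6. Carrier weight 0.69, SE 0.144. Bias = 0.69 × d/6 = 0.115d.

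**Case 3. Both groups close and are pooled.** Active 450 early + 225 late; placebo 225 + 225. Late shares 1/3 and 1/2. Bias = d/6. SE = 1.92 × √(1/472.5 + 1/315) = 0.140.

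Two-sided Type I error (nominal 0.05):

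| Case | d = 0.1 | d = 0.3 | d = 0.5 |
|---|---|---|---|
| 1 | 0.053 | 0.077 | 0.126 |
| 2 | 0.051 | 0.057 | 0.068 |
| 3 | 0.052 | 0.065 | 0.092 |

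In Case 1 the bias at d = 0.5 is 0.14 points, 28% of the 0.5 target.

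**Timing of closure.** At d = 0.5, with closure after a quarter, half or three quarters of enrolment, Case 1 simulated gives 0.120, 0.120 and 0.075, and Case 3 by formula gives 0.081, 0.092 and 0.068.

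**What is unaffected.** With d = 0 the bias is zero in every case. Randomised low dose against placebo has equal late shares if their allocation stays equal, so its bias is zero for any d.

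**The case against.** Much can be said for the plan. Closure is contingent, and an SAP that is not shown may restrict the comparison or add a covariate. The reasoning in Section 16.2.2.2 is standard for selection driven by interim data. Baseline CDR-SB with its time interaction, MMSE and ApoE status absorb part of any change in case mix. Section 5.3.2 of the latest version is not shown, so its closure wording can be read only in versions 1.0 to 3.0.

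The evidence for a trend is also thin. Between versions 1.0 and 2.0 some entry criteria changed: an HbA1c limit of 7% gave way to investigator judgement, and the washout after a disease-modifying study went from 26 weeks to 12 months. The RBANS criterion only gained a note naming the index. The separate blinded raters were there from version 1.0. Nothing ties these changes to a closure date or supports a particular value of d.

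A reader might infer that any time trend breaks Type I control, that the whole trial moves from 1:1:1 to 1:1, or that every comparison is affected. The documents do not support this. At d = 0.1 the error is at most 0.053 in the cases above. Only the closed stratum changes unless both close, and the 1:1 ratio is itself an inference. Low dose against placebo keeps its concurrent control on that same inference. The largest figures also depend on one reading of Table 12, which does not say whether carriers randomised to low dose join revised High.

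What remains is that the protocol does not leave the matter open. It asserts that no adjustment is needed, on a ground that does not cover non-concurrent placebo.

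**Conclusion.** The point holds as a limited correction. The sentence in Section 16.2.2.2 claims more than its premise supports, and following it after a closure can give a biased contrast for the revised High or pooled regimen. Under closure halfway, Type I error is close to nominal for a shift of 0.1 and between 0.068 and 0.126 for a shift of 0.5, depending on which groups close and how Table 12 is read. The bias can run for or against the drug. These sizes rest on an assumed shift, closure time, carrier share and later allocation. The direction of the argument does not, except that with no shift there is no bias. The point is worth settling before any closure, because the choice is harder to defend afterwards.

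**What to change.** In Section 16.2.2.2, limit the Type I statement to selection on efficacy data. Add that, if a high-dose group is closed, the MMRM for the affected comparison includes a term for randomised before or after closure, with its interactions with ApoE status and visit. State also whether carriers randomised to low dose belong to revised High in Table 12. Allocation is constant within each period, so the term handles gradual drift as well as a step.

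The cost is small and arises only if a group closes. For carrier closure halfway, in a linear model fitted to all three arms, SE rises from about 0.172 to 0.178 and power for a 0.5 difference falls from about 0.83 to 0.80. In simulation the term brings Type I error back to 0.045 to 0.057 at closure halfway, nominal within simulation error.

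Restricting the closed regimen to concurrent placebo also removes the bias but costs more. If both groups close halfway and the randomised high-dose arm is taken alone, there are 157.5 evaluable on high dose. Power is Φ(0.5/[1.92√(1/157.5 + 1/315)] − 1.96) = 0.76 with all placebo and no trend, and Φ(0.5/[1.92√(2/157.5)] − 1.96) = 0.64 with concurrent placebo only. That is better kept as a sensitivity analysis.
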